Sensitivity Analysis: A sensitivity analysis will be conducted to explore the impact of missing data in the primary efficacy analysis. Details will be provided in the statistical analysis plan.

Secondary and Exploratory Efficacy Analysis: The continuous secondary efficacy endpoints will be analyzed using an ANCOVA method or a mixed model for repeated measures. For the proportion of responders, defined as 50% or more reduction from baseline in the weekly average number of CH attacks, data will be analyzed using a Cochran-Mantel-Haenszel test stratified by baseline preventive medication use (yes/no).

Multiple Comparisons and Multiplicity: Hochberg’s step-up method will be implemented to test primary and secondary endpoints while controlling the overall type 1 error rate at 0.05.

Safety Analyses: All adverse events will be coded using the Medical Dictionary for Regulatory Activities. Each patient will be counted only once in each preferred term or system organ class category for the analyses of safety. Summaries will be presented for all adverse events (overall and by severity), adverse events determined by the investigator to be related to test IMP (ie, reasonable possibility, see Section 7.1.4) (defined as related or with missing relationship) (overall and by severity), serious adverse events, and adverse events causing withdrawal from the study. Patient listings of serious adverse events and adverse events leading to withdrawal will be presented.

The use of concomitant medications will be summarized by therapeutic class using descriptive statistics. Concomitant medications will include all medications taken while the patient is treated with the test IMP.

Changes in laboratory, ECG, and vital signs measurements data will be summarized descriptively. All values will be compared with prespecified boundaries to identify potentially clinically significant changes or values, and such values will be listed.

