3. STUDY DESIGN

3.1. General Design and Study Schematic Diagram

This is a 13-week, multicenter, randomized, double-blind, double-dummy, placebo-controlled, parallel-group study to compare the safety, and efficacy of 2 dose regimens of fremanezumab versus placebo in adult patients for the prevention of ECH. The study will consist of a screening visit, a run-in period lasting at least 1 week (+3 days), and a 12-week double-blind treatment period. During the course of any CH attack, patients will be allowed to use acute medications to treat acute headaches, as needed (PRN).

Patients will complete a screening visit (visit 1) after providing written informed consent, and eligible patients will enter a run-in period lasting at least 1 week (+3 days) during which they will enter baseline CH attack information into an electronic diary device daily. Patients will return to the study center after completing the run-in period (visit 2 [week 0]). Patients who had at least 7 CH attacks during the run-in period and who continue to meet eligibility criteria (including entry of CH attack information in an electronic diary demonstrating compliance for 85% of days during the run-in period) will be randomly assigned at visit 2 (week 0) in a 1:1:1 ratio to 1 of 3 treatment groups as follows:

- fremanezumab 900-mg iv loading dose group: fremanezumab at 900 mg administered via an approximately 1-hour iv infusion at visit 2 (week 0) followed by fremanezumab at 225 mg administered as single sc injections (225 mg/1.5 mL) at visits 3 and 4 (weeks 4 and 8, respectively)
- fremanezumab 675-mg sc quarterly group: fremanezumab at 675 mg administered as 3 sc injections (225 mg/1.5 mL) at visit 2 (week 0) followed by placebo administered as single sc injections at visits 3 and 4 (weeks 4 and 8, respectively)
- placebo group: placebo administered via an approximately 1-hour iv infusion and as 3 sc injections at visit 2 (week 0) followed by placebo administered as single sc injections at visits 3 and 4 (weeks 4 and 8, respectively)

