9.1. Sample Size and Power Considerations

A sample size of 258 patients (86 evaluable patients completing the study per treatment group) will provide at least 90% power to detect a treatment difference of 1 CH attack in the weekly average (assuming a common standard deviation [SD] of 2 CH attacks) at a 2-sided alpha level of 0.05. Assuming a 14% discontinuation rate, approximately 300 patients will be randomized in the trial.

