
Hochberg’s step-up method will be implemented to test primary and secondary endpoints while controlling the overall type 1 error rate at 0.05. The treatment comparisons will be for the fremanezumab 900-mg iv loading dose group versus placebo [H_{01}] and the fremanezumab 675-mg sc quarterly group versus placebo [H_{02}]. According to Hochberg step-up method, the rules of multiple comparisons for 2 null hypotheses for the primary endpoint are as follows:–Details will be provided in the statistical analysis plan.
 
If the resulting 2-sided p-values from both comparisons are ≤ 0.05 (reject both null hypotheses), then the next comparison of interest will be interpreted inferentially at the alpha level of 0.05 and statistical significance will be claimed for both active dose groups. Testing of secondary efficacy measures will be continued.
 
If the resulting 2-sided p-value from 1 of comparisons is >0.05 (fail to reject the null hypothesis) and the other resulting 2-sided p-value is ≤ 0.025 ($\alpha/2=0.025$; reject the null hypothesis), then the result from the comparison with p-value ≤ 0.025 will be interpreted inferentially at the alpha level of 0.05 and statistical significance will be claimed for this active dose group. No other comparison(s) will be interpreted inferentially.
 
If the resulting 2-sided p-values from both comparisons are >0.05 (fail to reject both null hypotheses), then no statistical significance will be claimed and no comparisons will be interpreted inferentially.
 
If the resulting 2-sided p-values from both comparisons for the primary endpoint are ≤ 0.05 (reject both hypotheses; case 1 as described above), testing of secondary efficacy measures will proceed at an error rate of 0.05 in the sequential manner as specified in Section 2.1. The same testing rules as described above will be followed. This process will continue either until all comparisons of interest for secondary endpoints are
	
Hochberg’s step-up method will be implemented to test primary and secondary endpoints while controlling the overall type 1 error rate at 0.05. The treatment comparisons will be for the fremanezumab 900-mg iv loading dose group versus placebo [H_{01}] and the fremanezumab 675-mg sc quarterly group versus placebo [H_{02}]. According to Hochberg step-up method, the rules of multiple comparisons for 2 null hypotheses for the primary endpoint are as follows:
 
If the resulting 2-sided p-values from both comparisons are ≤ 0.05 (reject both null hypotheses), then the next comparison of interest will be interpreted inferentially at the alpha level of 0.05 and statistical significance will be claimed for both active dose groups. Testing of secondary efficacy measures will be continued.
 
If the resulting 2-sided p-value from 1 of comparisons is >0.05 (fail to reject the null hypothesis) and the other resulting 2-sided p-value is ≤ 0.025 ($\alpha/2=0.025$; reject the null hypothesis), then the result from the comparison with p-value ≤ 0.025 will be interpreted inferentially at the alpha level of 0.05 and statistical significance will be claimed for this active dose group. No other comparison(s) will be interpreted inferentially.
 
If the resulting 2-sided p-values from both comparisons are >0.05 (fail to reject both null hypotheses), then no statistical significance will be claimed and no comparisons will be interpreted inferentially.
 
If the resulting 2-sided p-values from both comparisons for the primary endpoint are ≤ 0.05 (reject both hypotheses; case 1 as described above), testing of secondary efficacy measures will proceed at an error rate of 0.05 in the sequential manner as specified in Section 2.1. The same testing rules as described above will be
	
Details about multiple comparisons and multiplicity added for clarification.

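### Section 9.1's 90% power holds for one comparison at an unadjusted 0.05; under the trial's Hochberg rule it is about 89% for a given dose and 84% for both doses

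*Protocol*

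**What the plan says.** Protocol Section 9.1 sets the sample size in two sentences. The first claims that 86 evaluable completers per arm, 258 in all, "will provide at least 90% power to detect a treatment difference of 1 CH attack in the weekly average". The inputs behind that claim are an SD of 2 attacks in every arm and a test carried out "at a 2-sided alpha level of 0.05". The second sentence allows for 14% of patients stopping early and so arrives at about 300 randomized. Neither sentence mentions that two doses are compared with placebo.

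The design has two active arms and one shared placebo arm; patients are "randomly assigned at visit 2 (week 0) in a 1:1:1 ratio to 1 of 3 treatment groups" (Protocol Section 3.1).

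The synopsis, under Multiple Comparisons and Multiplicity, names Hochberg's approach: this "step-up method will be implemented to test primary and secondary endpoints while controlling the overall type 1 error rate at 0.05". Protocol Section 9.6 is redacted in its body, but the new-wording column for that section in the summary of Amendment 02 (Protocol Section 16.1) spells out the rule:

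- If both primary p-values are at most 0.05, both doses succeed and the secondary endpoints are tested in sequence.
- If one p-value is above 0.05 and the other is at most 0.025, "statistical significance will be claimed for this active dose group" and formal testing ends.

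SAP Section 2.4, on sample size, is redacted, and no multiplicity text is visible in the SAP.

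**The concern.** The power in Section 9.1 belongs to a test that the trial does not run on its own. Under Hochberg a dose is judged at 0.05 only when the other dose also reaches 0.05; otherwise it must reach 0.025. That costs power for any given dose. Power for both doses together is lower again.

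The sample size has almost no margin to absorb the cost: 86 is the smallest number per arm that reaches 90% for one unadjusted t-test.

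At stake is what a reader believes the trial can deliver. Someone reading Section 9.1 would put the risk of missing a truly effective dose at about 10%. If only one regimen works, the risk at 86 per arm is about 15%. If both work as planned, there is about a 16% chance that one of them misses, and then none of the six secondary efficacy endpoints is formally tested.

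**Working it through.** **Inputs.** From Protocol Section 9.1: n = 86 per arm, difference 1 attack per week, SD 2, two-sided alpha 0.05, 14% discontinuation. From Section 3.1: 1:1:1 allocation with a shared placebo arm, so the two dose-placebo contrasts have correlation 0.5. From the synopsis and the Amendment 02 wording: the Hochberg rule.

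**Step 1: reproduce the stated figure.** The standard error of a difference is 2 × √(2/86) = 0.305, so the noncentrality is 1/0.305 = 3.28.

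- Normal approximation, alpha 0.05: 90.6%.
- Noncentral t, 170 df (two groups): 90.3%. With 255 df (error pooled over three groups): 90.4%.
- Noncentral t at 85 per arm, two groups: 89.99%. So 86 is the minimum for one comparison.
- Discontinuation: 258/(1 − 0.14) = 300.

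The stated power and the 300 both reproduce.

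**Step 2: apply the Hochberg rule.** Write p1 and p2 for the two primary p-values.

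- Both doses win if p1 ≤ 0.05 and p2 ≤ 0.05.
- Dose 1 wins if both win, or if p1 ≤ 0.025.
- At least one dose wins if dose 1 wins or dose 2 wins.

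This was simulated with 2,000,000 trials, a shared placebo arm and t-tests on 255 pooled df. Results at 86 per arm:

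| Meaning of power | Truth | Power |
|---|---|---|
| One comparison, unadjusted 0.05 | difference 1 | 90.3% |
| A given dose | both doses differ by 1 | 89.3% |
| A given dose | other dose has no effect | 84.9% |
| Both doses | both differ by 1 | 84.0% |
| At least one dose | both differ by 1 | 94.6% |

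Two checks agree. One comparison at a fixed 0.025 has 84.6% power (255 df), close to the figure when the other dose does nothing. And the chance of at least one win equals twice the given-dose power minus the both-dose power: 2 × 89.3 − 84.0 = 94.6.

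**Step 3: vary the number analysed.** The 86 are completers of the study. The primary endpoint uses weeks 0 to 4, and the full analysis set in SAP Section 3.3 requires one dose and at least 10 days of efficacy data in the first 4 weeks. The analysed number may therefore lie anywhere from 86 up to the 100 randomized per arm. The documents give no expected size, so this range is an assumption.

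| Per arm | Given dose, both work | Given dose, other null | Both doses |
|---|---|---|---|
| 86 | 89% | 85% | 84% |
| 95 | 92% | 89% | 88% |
| 100 | 93% | 90% | 89.8% |

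When both doses work, 90% for a given dose needs about 89 per arm, and 90% for both doses needs about 101.

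**The case against.** The strongest reply is that Section 9.1 makes no mistake. It names its alpha, and the power follows from it. That stands. A reader might infer a slip of arithmetic, but the documents do not support that; what is missing is a definition of power and an allowance for multiplicity.

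A reader might also infer that Hochberg pushes power below 90% however it is defined. It does not. The rule allows a claim on one dose alone, and the primary objective is the efficacy of fremanezumab rather than of both regimens. On that reading power is about 95%.

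The loss for a given dose when both work is only about 1 point. The 85% needs a dose with no effect at all, which Section 9.1 does not posit, and Section 9.1 never claims 90% for both doses. All of this stands. The case rests mainly on the 84%, because of its hold over the secondary endpoints.

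The planned ANCOVA may recover some power. If the SD of 2 is before adjustment, a variance reduction of 1 − 86/89 = 3.4% brings the given-dose figure to 90%, and 1 − 86/101 = 14.9% does so for both doses. If the SD of 2 is already the residual SD, there is no gain. The protocol does not say which it is.

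It is tempting to say that using the full analysis set restores 90% throughout. It does not quite: both-dose power is 89.8% even if all 100 per arm are analysed, and no document states that size.

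Finally, SAP Section 2.4 is redacted and may deal with multiplicity. That cannot be judged, but the visible sentence in Section 9.1 does not.

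**Conclusion.** The concern holds in a limited form. Section 9.1's figure is correct for one comparison at an unadjusted two-sided 0.05 (90.3%) and makes no allowance for the Hochberg rule. Under that rule, at 86 per arm, 90% is missed by about 1 point for a given dose when both work, by about 5 points when the other dose is null, and by about 6 points for both doses. It is exceeded, at about 95%, for at least one dose when both work.

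These figures assume a true difference of 1, an SD of 2, equal arms, no gain from covariates, and the multiplicity rule as shown in the Amendment 02 wording. They do not show that the trial is too small. They show that the stated power does not describe the planned test.

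**What to change.** Rewrite the power statement in Protocol Section 9.1, and align SAP Section 2.4 if its redacted text says the same:

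1. Say which power is meant: a given dose, both doses, or at least one dose.
2. Report it under Hochberg at 86 per arm: about 89% for a given dose if both work, 85% if the other dose is null, 84% for both, and 95% for at least one. Note that the both-dose figure is also the chance that secondary testing opens.
3. Show the range for an assumed full analysis set of 86 to 100 per arm, labelled as an assumption.
4. State whether the SD of 2 is before or after ANCOVA adjustment.

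The cost is a few sentences. No patients are added, and neither the tests nor the conduct of the trial change. The stated power becomes somewhat less favourable for a given dose and clearly less so for both.

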9.2. Analysis Sets

9.2.1. Intent-to-Treat Analysis Set

The intent-to-treat (ITT) analysis set will include all randomized patients.

In the ITT analysis set, treatment will be assigned based on the treatment to which patients were randomized, regardless of which treatment they actually received.

9.2.2. Safety Analysis Set

The safety analysis set will include all randomized patients who receive at least 1 dose of IMP.

In the safety analysis set, treatment will be assigned based on the treatment patients actually received, regardless of the treatment to which they were randomized, unless otherwise specified.

9.2.3. Full Analysis Set

The full analysis set will include all patients in the ITT analysis set who receive at least 1 dose of IMP and have at least 1 postbaseline efficacy assessment on the primary endpoint.

9.2.4. Per-Protocol Analysis Set

The per-protocol (PP) analysis set is a subset of the ITT analysis set including only patients without any important protocol deviations. Important protocol deviations will be determined before unblinding/database lock.

In the PP analysis set, treatment will be assigned based on the treatment patients actually received, regardless of the treatment to which they were randomized.

9.3. Data Handling Conventions

Efficacy variables from patients who do not have diary entries completed for the entire study period will be imputed. Detailed data imputation rules will be described in the statistical analysis plan.

9.3.1. Handling Withdrawals and Missing Data

Efficacy variables from patients who do not have diary data completed for the entire study period will be imputed. For the analyses based on the proportion of responders, patients who are terminated from the study early will be considered as non-responders. For patients who complete the study and have intermittent missing days in the e-diary, data will be prorated to 7 days. Details will be provided in statistical analysis plan.

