9.5.2. Secondary Endpoints

The secondary efficacy endpoints to further demonstrate efficacy are as follows:

- the proportion of patients with a $\geq 50\%$ reduction from baseline (run-in period) in the weekly average number of CH attacks during the 4-week period after the first dose of the IMP, ie, based on week 0 to 4 data
- the mean change from baseline (run-in period) in the number of CH attacks during the 12-week period after administration of the first dose of the IMP, ie, based on week 0 to 12 data
- the mean change from baseline (run-in period) in the number of CH attacks during the 4-week period after administration of the third dose of the IMP, ie, based on week 8 to 12 data
- the mean change from baseline (run-in period) in the weekly average number of days with use of cluster-specific acute headache medications (triptans and ergot compounds) during the 12-week period after administration of the first dose of the IMP, ie, based on week 0 to 12 data
- the mean change from baseline (run-in period) in the weekly average number of days oxygen is used to treat ECH during the 12-week period after administration of the first dose of the IMP, ie, based on week 0 to 12 data
- assessment of patient’s perceived improvement, as measured by the PPSI at 1, 4, 8, and 12 weeks after administration of the first dose of the IMP relative to baseline (day 0)

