6.3. Secondary Efficacy Endpoints and Analyses

The secondary efficacy endpoints are listed in Section 1.2. Analyses will be based on the FAS and PP analysis sets [REDACTED].

As exploratory analyses, endpoints analyzed using an ANCOVA method will be also analyzed using MMRM method in a manner analogous to the analysis as described in Section 6.2.3.2. The analysis windows will be specified in the related section.

6.3.1. Proportion of Patients with a $\geq 50\%$ Reduction from Baseline in the Weekly Average Number of CH Attacks During the 4-Week Period After the First Dose of the IMP

This secondary efficacy endpoint will be analyzed using Cochran-Mantel-Haenszel (CMH) test stratified by baseline preventive medication use (yes or no). Descriptive statistics (count and percent) and p-value for Row Mean Scores difference will be presented.

CH attacks will be derived from the e-diary data as described in Section 6.1.1. The analysis will be based on weeks 1 to 4 analysis window which will be derived using the algorithm described in Section 6.1.3. The weekly average number of CH attacks will be calculated based on data available and prorated to 7 days using formula [1]. Missing data handling methods are provided in Section 6.1.4.2.

The proportion of reduction for a patient will be calculated using formula [2]. Responders will be those with $\geq 50\%$ reduction.

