15. STATISTICAL SOFTWARE

All data listings, summaries, and statistical analyses will be generated using SAS[®].

**16. CHANGES TO ANALYSES SPECIFIED IN THE STUDY
PROTOCOL**

None.

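### Protocol 9.3.1 puts no time limit on its early-termination rule, so as worded a patient who leaves after week 4 is a non-responder on the week 0–4 endpoint

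*Protocol*

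**What the plan says.** **The rule.** Protocol 9.3.1 covers all analyses of the proportion of responders: "patients who are terminated from the study early will be considered as non-responders". It names no window. The next sentence restricts proration to completers: "For patients who complete the study and have intermittent missing days in the e-diary, data will be prorated to 7 days". The section then leaves details to the SAP.

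**The endpoint.** The first secondary endpoint in Protocol 9.5.2 is the proportion of patients with at least a 50% reduction in weekly attacks, "during the 4-week period after the first dose of the IMP, ie, based on week 0 to 4 data". Protocol 3.1 describes "a run-in period lasting at least 1 week (+3 days), and a 12-week double-blind treatment period", so a patient can leave up to eight weeks after the responder window has closed.

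**The SAP.** Section 6.3.1 computes the weekly average for this endpoint from whatever diary data exist, scaled to 7 days by formula [1]. It classes a reduction of 50% or more as response and refers to 6.1.4.2 for missing data. The text of 6.1.4.2 is redacted. Section 6.1.4.1 uses available data in the same way for the primary endpoint. Section 3.3 removes patients with fewer than 10 diary days in the first 4 weeks from the full analysis set (FAS).

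**The concern.** Take a patient with 28 complete diary days, a 70% reduction, and withdrawal in week 9. Nothing about weeks 0–4 is missing. The primary analysis uses this patient's data as recorded. Under the wording of Protocol 9.3.1, the responder analysis sets the same data aside and records a failure.

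Late exit need not reflect treatment failure. Protocol 4.3, 5.9.2 and 7.4.1.1 also withdraw patients for pregnancy, a broken blind, prohibited medication or a sponsor request. None of these changes what happened in the first four weeks.

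The stake is the comparison on the first-listed secondary endpoint. Equal late dropout dilutes a true difference. Unequal late dropout moves the estimate for reasons outside the endpoint's window.

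**Working it through.** **1. The plan's own figure.** Protocol 9.1 sizes the trial on the primary endpoint: difference 1, SD 2, "at a 2-sided alpha level of 0.05", at least 90% power. The normal formula gives n = 2 × (1.960 + 1.282)² × 2² / 1² = 84.1, so 85 per arm. The t-test version gives 85.03, so 86. Power at 86 per arm is 0.903 (t) to 0.906 (normal). Dropout: "Assuming a 14% discontinuation rate, approximately 300 patients will be randomized in the trial"; 258 / 0.86 = 300, so about 42 patients are expected to leave. The figures reproduce. No power is stated for the responder endpoint.

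**2. Inputs for the illustration.**
- From the documents: 14% discontinuation, about 100 randomized per arm, two-sided 0.05.
- Assumed, because the documents give none of these: response of 40% on placebo and 60% on active; a share f of the dropout falling after week 4; late leavers responding at the same rate as other patients in their arm.

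**3. Equal late dropout.** With d = 0.14 × f, each arm's observed rate is p × (1 − d), so the difference is multiplied by (1 − d).

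Power = Φ{[Δ − 1.96 √(2p̄(1 − p̄)/n)] / √([p₁(1 − p₁) + p₂(1 − p₂)]/n)}, n = 100 per arm.
- No overwriting: (0.200 − 1.96 × 0.0707) / 0.0693 = 0.886, power 0.81.
- d = 0.14: (0.172 − 1.96 × 0.0700) / 0.0690 = 0.504, power 0.69.

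| Share of dropout after week 4 | d | Patients of 300 | Observed rates | Difference | Power |
|---|---|---|---|---|---|
| none | 0 | 0 | 40.0% vs 60.0% | 20.0 | 81% |
| 1/3 | 4.7% | 14 | 38.1% vs 57.2% | 19.1 | 77% |
| 2/3 | 9.3% | 28 | 36.3% vs 54.4% | 18.1 | 73% |
| all | 14% | 42 | 34.4% vs 51.6% | 17.2 | 69% |

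Other assumed rates behave alike: 30% vs 50% goes from 83% to between 80% and 73%; 50% vs 70% goes from 83% to between 78% and 69%.

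**4. Unequal late dropout.** Assume total dropout of 9% in one arm and 19% in the other, two thirds of it after week 4, so d is 6.0% and 12.7%.
- Active arm has the 19%: 0.60 × 0.873 − 0.40 × 0.940 = 0.524 − 0.376 = 14.8 points.
- Placebo has the 19%: 0.60 × 0.940 − 0.40 × 0.873 = 0.564 − 0.349 = 21.5 points.
- No true effect, common rate p: the gap is p × (0.127 − 0.060), which is 2.7 points at p = 40% and 4.0 points at p = 60%.

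**The case against.** **The operative rule cannot be read.** The protocol defers to the SAP, SAP 6.3.1 defers to 6.1.4.2, and 6.1.4.2 is redacted. The SAP's introduction says that it prevails where the two documents differ. This stands: the public text neither confirms nor excludes a rule already tied to the 4-week window.

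A reader might infer that the protocol rule must carry over because SAP Section 16 ("CHANGES TO ANALYSES SPECIFIED IN THE STUDY" Protocol) says there are none. That inference fails. The SAP changes several protocol rules without listing them: the FAS goes from at least one postbaseline assessment to at least 10 diary days; the per-protocol set goes from treatment received to treatment randomized; region goes from US to US/Canada; and proration is no longer confined to completers.

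A reader might also infer that SAP 6.3.1 contradicts the protocol. It need not: computing an average from available data and then applying a missing-data rule can be successive steps.

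**Not every early terminator is scored a failure.** Under the SAP, those with fewer than 10 diary days in the first four weeks leave the FAS altogether. This also stands, but it does not touch the patient who withdraws after week 4.

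**Discontinuation as failure is a recognised conservative choice.** True, and if study retention is meant to be part of response, the endpoint should say so. This endpoint is defined on week 0–4 data alone.

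**The size is assumed.** True. Lack of efficacy is a named reason for withdrawal (Protocol 3.4 and 4.3), and late leavers who were already non-responders lose nothing by the rule. The dilution would then be smaller than the table shows.

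**Conclusion.** The point holds as a defect in the protocol's wording: an unlimited termination rule is attached to an endpoint whose window closes eight weeks before the study ends. Whether the final analysis would apply it depends on the redacted SAP 6.1.4.2, so the documents do not support saying that such patients will in fact be overwritten.

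If the rule is applied as worded, the loss is moderate: 0.9 to 2.8 points off an assumed 20-point difference, and power of 77% to 69% in place of 81%. This rests on the assumed response rates, the assumed dropout timing, and late leavers responding like everyone else. With unequal late dropout the direction is not fixed.

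The primary endpoint is unaffected. A reader might infer that failing this endpoint would block every later secondary test. The current Protocol 9.6 is redacted and that sequence is visible only in the Amendment 02 change summary, so the conclusion here does not lean on it.

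**What to change.** First check the unredacted SAP 6.1.4.2. Before unblinding, amend Protocol 9.3.1, and SAP 6.1.4.2 if it repeats the rule, so that non-response applies only to patients who terminate before the end of the endpoint's own window.

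For the week 0–4 responder endpoint:
- FAS patients who terminate before day 28 remain non-responders. This matters because a patient who leaves on day 11 could otherwise count as a 4-week responder on prorated data.
- Patients who complete the 4-week window are scored from their observed data, prorated by formula [1], whatever happens later.

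Keep the study-termination rule for the 12-week responder endpoints. If 6.1.4.2 is already limited to the window, only the protocol sentence needs aligning.

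The cost is about one sentence per document. The downside is that the endpoint becomes slightly less conservative for late withdrawals.
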